3.1.3 Follow-up treatment of subjects with clinically significant toxicity

In the observation period of tolerability, the subjects with clinically significant toxicity may receive subsequent combination therapy of SHR-1210 and apatinib based on the investigator's judgment after they have recovered from toxicity: interrupt, reduce (for subjects using 500 mg/d or 375 mg/d apatinib) or discontinue apatinib administration according to the dose modification principles, or discontinue the treatment. Subjects will also be followed up and their data will be collected according to the study procedure.

3.2 Pharmacokinetic Study

3.2.1 Study procedure and arrangement of blood sampling points

After the completion of the tolerability observation, 10 to 12 subjects will be enrolled in each dose group for an expanded pharmacokinetic study. In the expanded pharmacokinetic study, one dose of SHR-1210 will be administered on D1 of Cycle 1 (28 d) via intravenous infusion. Pharmacokinetic blood sampling will be performed within 0.5 h pre-dose, and at 5 min (± 5 min), 2 h (± 10 min) and 6 h (± 10 min) after the administration of SHR-1210 on D1, and on D2 (24 h, ± 1 h), D3 (48 h, ± 1 h), D8 (168 h, ± 1 h), D15 (336 h, ± 1 h) and D22 (504 h, ± 1 h), with 3 mL of blood collected at each time point. After the completion of pharmacokinetic blood sampling on D22, the administration of apatinib mesylate tablets (250 mg/tablet·1 tablet, 375 mg/tablet·1 tablet or 250 mg/tablet·2 tablets) will be started on the same day and continues at a administration frequency of once a day. Pharmacokinetic blood sampling will be performed within 0.5 h pre-dose on D28 and at 0.5 h (± 5 min), 1 h (± 5 min), 2 h (± 5 min), 3 h (± 5 min), 5 h (± 10 min), 8 h (± 10 min), 12 h (± 10 min), and 24 h (± 1 h) after the administration, with 3 mL of blood collected at each time point.

On D1 of Cycle 2, PK blood sampling will be performed within 0.5 h before the administration of SHR-1210, and at 5 min (± 5 min), 2 h (± 10 min) and 6 h (± 10 min) on D1, D2 (24 h, ± 1 h), D3 (48 h, ± 1 h), D8 (168 h, ± 1 h), and D15 (336 h, ± 1 h) post-administration, with 3 mL of blood collected at each time point. On D28 of Cycle 2, PK blood sampling will be performed within 0.5 h before the administration of apatinib, and at 0.5 h (± 5 min), 1 h (± 5 min), 2 h (± 5 min), 3 h (± 5 min), 5 h (± 10 min), 8 h (± 10 min), 12 h (± 10 min), and 24 h (± 1 h) post-administration, with 3 mL of blood collected at each time point.

There will be a total of 35 blood sampling points. After the blood sampling is completed, the subjects will continue to receive the study treatment until an event meeting the criteria of study termination occurs.

If a subject interrupts the administration of apatinib during the period of pharmacokinetic blood sampling due to adverse events and if the interruption of apatinib occurs during C1D22-D28, the subject will not be subject to pharmacokinetic blood sampling in the future and will be deemed as not completing the pharmacokinetic study; if the interruption of apatinib occurs during C2D23-C2D28, the pharmacokinetic blood sampling will not be carried out on C2D28. Then, after the administration of apatinib is resumed and continued for 7 days, the administration of apatinib and the blood sampling will be carried out on D7 according to the administration method of apatinib (administration under fasting) and the time points of blood sampling specified for C2D28.

If the administration of SHR-1210 can not be carried out normally during C2D1-C2D28 due to adverse events, the pharmacokinetic blood sampling will not be performed starting from C2D1 and the subject will be deemed as not completing the pharmacokinetic study.

The administration of SHR-1210 should be performed at the scheduled time on C2D1 of the pharmacokinetic study, and no time window for delayed administration is set. The delayed administration of SHR-1210 on C2D15 is allowed as long as the time of administration does not exceed the planned time by more than 3 days.

Substitution of subjects is required for those who have not completed the pharmacokinetic study to ensure that 10 to 12 subjects can complete the pharmacokinetic study.

Subjects who have not completed pharmacokinetic blood sampling may continue to receive the study drug according to the investigator's judgment until an event meeting the criteria for treatment discontinuation occurs.

3.2.2 Blood sample processing and testing

Blood sampling will be carried out before and after the administration of SHR-1210 on D1-D22 of Cycle 1 and D1-D15 of Cycle 2, with 3 mL of whole blood collected into a coagulation tube at each blood sampling time point, and the coagulation tube should be inverted several times to mix the blood sample evenly. After placing the blood sample at room temperature for 30 min, it should be centrifuged at 4 °C and 1500 g (centrifugal force) for 10 min; then, the supernatant will be aliquoted into 2 tubes (about 500 µL per tube).

Blood sampling will be carried out before and after the administration of apatinib on D28 of Cycle 1 and D28 of Cycle 2, with 3 mL of whole blood collected into an anti-coagulation tube at each blood sampling time point, and the anti-coagulation tube should be inverted several times to mix the blood sample with the anticoagulant in the tube. Blood samples will be centrifuged within 30 min after blood sampling at 4 °C and 1500 g (centrifugal force) for 10 min; the supernatant will be aliquoted into 2 tubes (at least 500 µL per tube).

After being well-marked, the separated plasma/serum samples are temporarily kept in a freezer at -20 °C or below, or at -60 °C for a longer period prior to future testing.

Each sample will be assigned with a unique sample number. The actual date and time of blood sampling as well as the exact time of drug administration should be recorded on the PK blood sampling page of the eCRF. The problems encountered during blood sampling should be noted in the eCRF.

3.3 Collection of Biomarker Samples

For all enrolled subjects, their blood samples will be collected at baseline. For subjects showing CR/PR during the study, their blood samples will be collected during the first evaluation of CR/PR and the first evaluation of PD, with 10 mL of blood samples collected each time (14 mL of blood will be collected at baseline and divided into two tubes, with 10 mL in one tube and 4 mL in the other tube). These blood samples will be sent to the central laboratory for blood-based detection of tumor mutation burden (TMB), while the detection of circulating tumor cells (CTC) and the detection of PD-L1 based on circulating tumor cells (CTC) will also be performed in the baseline period. See the central laboratory manual for blood sampling, disposal, and transportation.

For subjects participating in the Stage II of the study, their tumor tissue samples will be collected at baseline. Among these tumor tissue samples, 3-5 slices of 3-4 µm thick paraffin tissue sections will be sent to the central laboratory for the detection of levels of PD-L1 and tumor-associated macrophages (TAM) in tumor tissues; 5-8 slices of 5-8 µm thick tumor biopsy samples or paraffin tissue sections collected before the first dose will also be sent to the central laboratory

for the detection of TMB level in tumor tissues. The biopsy samples can be directly sent to the central laboratory through cold chain transportation. Paraffin blocks can be directly sent to the central laboratory without mounting onto slides. See the central laboratory manual for tissue sampling and transportation.

In order to avoid the impact of previous treatment on tumor mutation burden, the tumor tissue samples should be collected from biopsy or surgical resection carried out at a time point closest to the first dose for the detection of TMB levels.

4 RANDOMIZATION AND BLINDING

4.1 Randomization

Subjects will not be randomized in the tolerability observation period of Stage I. The tolerability observation will be carried out first for the dose group of 250 mg apatinib, oral, q.d. + 200 mg SHR-1210, IV, q2W. After it is confirmed that the dose group of 250 mg apatinib, oral, q.d. + 200 mg SHR-1210, IV, q2W is safe and tolerable, the tolerability observation for the dose groups of 375 mg and 500 mg apatinib, oral, q.d. + 200 mg SHR-1210, IV, q2W will be carried out in sequence.

After completing the tolerability observation of a group, 10 to 12 additional subjects will be enrolled in each group for an expanded pharmacokinetic (PK) study.

If two doses are selected for the Stage II, the subjects enrolled in Stage II will be randomized in a 1:1 ratio using the randomization system provided by Jiangsu Hengrui Pharmaceuticals Co., Ltd. into two groups for observation.

4.2 Blinding

This study is an open-label study and does not involve blinding.

5 SUBJECT SELECTION AND WITHDRAWAL/DISCONTINUATION

5.1 Inclusion Criteria

Patients must meet all of the following criteria to be eligible for this study:

1. Male and female patients aged 18-70 years old;
2. Pathologically confirmed advanced (Phase IIIB and IV) non-small cell lung cancer with at least one measurable lesion that meets the RECIST v1.1 criteria and has not been treated locally;
3. Able to provide previous tumor samples or agree to cooperate with biopsy (Stage II);

4. Stage I: Patients who have undergone the second-line and above chemotherapy (at least one of the previous chemotherapy regimens is a platinum-based chemotherapy doublet regimen) but failed the treatment or showed recurrence. The patients harboring EGFR mutations and ALK gene abnormalities must have failed the treatment with an EGFR inhibitor or ALK inhibitor.

Stage II: Patients who have undergone only one previous platinum-based doublet chemotherapy but failed the treatment or showed recurrence, or patients in the stage of palliative treatment who have received no systemic treatment (only for cohort 4).

- a. The replacement of platinum drugs due to drug toxicity will be considered as one treatment regimen;
- b. Postoperative adjuvant chemotherapy will not be counted as one previous chemotherapy regimen if the time from the end of treatment to recurrence is > 6 months.

According to the type of driver gene mutations and pathological classification, the subjects will be divided into the following four cohorts:

Cohort 1. Patients with confirmed absence of mutations in EGFR 18-21 exons and ALK fusion genes (the histochemistry result of ALK D5F3 antibody is negative);

Cohort 2. Patients with confirmed presence of mutations in EGFR 18-21 exons or ALK fusion genes (the histochemistry result of ALK D5F3 antibody is positive). Carriers of sensitive EGFR mutations must have received at least one targeted treatment with EGFR tyrosine kinase inhibitors (EGFR-TKI) and failed the treatment. Carriers of positive ALK fusion genes must have failed the treatment of at least one targeted treatment with ALK tyrosine kinase inhibitor (ALK-TKI) (treatment failure: progressive disease or intolerable toxicity during the treatment);

Cohort 3. Imaging confirmed non-central squamous cell lung cancer or adenosquamous carcinoma primarily consisted of squamous cell carcinoma (pathologically confirmed).

Cohort 4. Non-squamous and non-small cell lung cancer with wild-type EGFR and ALK and with bTMB ≥ 1.54 muts/Mb or tTMB > 10 muts/Mb confirmed by central laboratory, and patients in the stage of a palliative treatment who have received no systemic treatment.

5. ECOG PS: 0-1;
6. Life expectancy ≥ 12 weeks;

7. Major organ functions must meet the following rules (not including the use of blood components or cell growth factors during screening):
 - Absolute neutrophil count $\geq 1.5 \times 10^9/L$;
 - Platelets $\geq 100 \times 10^9/L$;
 - Hemoglobin ≥ 9 g/dL;
 - Serum albumin ≥ 3 g/dL;
 - Thyroid stimulating hormone (TSH) \leq ULN (In the case of abnormalities, FT3 and FT4 levels should also be measured. If FT3 and FT4 levels are normal, the patient can be enrolled);
 - Total bilirubin \leq ULN;
 - ALT and AST $\leq 1.5 \times$ ULN;
 - AKP $\leq 2.5 \times$ ULN;
 - Serum creatinine $\leq 1.5 \times$ ULN or creatinine clearance ≥ 60 mL/min (using the standard Cockcroft-Gault formula, as shown in Appendix 3);
8. Female patients of a childbearing age who are not surgically sterilized should adopt a medically approved contraceptive measure (such as an intra-uterine contraceptive device, contraceptive pills or condoms) during the study treatment period and within 3 months after the end of the study treatment; female patients of a childbearing age who are not surgically sterilized must have a negative serum or urine HCG test result within 72 h prior to study enrollment, and must not be in the lactation period; male patients should be surgically sterilized or agree to use an appropriate contraceptive measure during the study period and within 3 months after the last dose of the study drug;
9. Patients must participate voluntarily, sign the informed consent form, have good compliance, and cooperate with follow-up visits.

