- [11] Hepatitis B, hepatitis C, and HIV tests: hepatitis B panel [If the test results are abnormal, viral replication (HBV DNA) test should be performed]; hepatitis C virus antibody (anti-HCV) test (If the test results are abnormal, virus titer should be tested); HIV antibody test.
- [12] Pregnancy test: The urine pregnancy test will be performed 72 h before the first dose for females of a childbearing age. If the result of the urine pregnancy test is positive, a serum pregnancy test shall be performed. If necessary, re-tests can be performed for confirmation.
- [13] If the subjects have previously been tested for EGFR mutations and ALK fusion gene, retests are not required; otherwise, the study site will perform relevant tests. If the subjects are positive for EGFR mutations, the test of ALK fusion gene will no longer be performed.
- [14] Adverse events: Adverse events will be collected from the time when the subjects sign the informed consent form. AEs unrelated to the study drugs will be collected to 30 days after the last dose. Treatment-related AEs will be collected until 90 days after the last dose of SHR-1210 or 30 days after the last dose of targeted anti-angiogenic therapy (whichever is longer). See the AE/SAE collection time limit in Section 8.3 for details.
- [15] Vital sign examination: Body temperature, respiration, pulse, blood pressure. The examination will be performed within 7 days before enrollment, on Day 1 and Day 15 of Cycle 1, Day 1 and Day 15 of subsequent cycles, upon completion of the study, and 30 days after treatment.
- [16] Physical examination and weight measurement: Examination of major body systems (head and face, skin system, lymph nodes, eyes, ears, nose, throat, oral cavity, respiratory system, cardiovascular system, abdomen, urogenital system, musculoskeletal system, nervous system and mental state) will be performed within 7 days before enrollment, on D1 and D15 of Cycle 1, D1 and D15 of subsequent cycles, upon completion of the study, and 30 days after the end of treatment. Body weight measurement will be started on D1 of Cycle 1 and performed on D1 of subsequent cycles, upon completion of the study, and 30 days after the end of treatment.
- [17] 12-Lead ECG: Performed within 7 days before enrollment, on Day 15 of Cycle 1, Day 1 and Day 15 of subsequent cycles, and upon completion of the study. Abnormalities in ECG must be confirmed twice via additional ECG tests.

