A single-arm/double-arm, multicenter, open-label clinical study.

According to the results of tolerability observation in Stage I and upon the discussion between the sponsor and the principal investigators, 250 mg of apatinib, q.d. oral + 200 mg of SHR-1210, IV, q2W are selected for the Stage II study.

Patients of advanced NSCLC who have failed first-line chemotherapy or patients of non-squamous and non-small cell lung cancer with a high tumor mutation burden (TMB) confirmed by the central laboratory will be enrolled in the Stage II study. According to the molecular and pathological classifications, the subjects are divided into:

Cohort 1. Non-squamous, non-small cell lung cancer with wild-type EGFR and ALK;

Cohort 2. Non-small cell lung cancer with EGFR mutation or ALK fusion gene rearrangement. The subjects harboring sensitive EGFR mutations and ALK fusion gene rearrangement must have failed the treatment of at least one EGFR inhibitor or ALK inhibitor;

Cohort 3. Non-central squamous cell lung cancer;

Cohort 4. Non-squamous and non-small cell lung cancer with wild-type EGFR and ALK and with bTMB ≥ 1.54 muts/Mb or tTMB > 10 muts/Mb confirmed by central laboratory.

The enrolled subjects are treated until the occurrence of any event that meets the criteria for discontinuation, so as to further evaluate the efficacy and safety of SHR-1210 in combination with apatinib in patients with advanced NSCLC.

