[Detection of EGFR mutations and ALK fusion gene] If the subjects have previously been tested for EGFR mutations and the ALK fusion gene, they do not need to be tested again. If the subjects have not been tested previously, the study site will carry out relevant tests. If the subjects are positive for EGFR mutations, the test of ALK fusion gene will no longer be performed.

[Adverse events] Adverse events will be recorded from the time when the subjects sign the informed consent form. AEs unrelated to the study drugs will be recorded to 30 days after the last dose. Treatment-related AEs will be collected until 90 days after the last dose of SHR-1210 or 30 days after the last dose of targeted anti-angiogenic therapy (whichever is longer). See the AE/SAE collection time limit in Section 8.3 for details.

[Blood pressure monitoring] The blood pressure measurement of subjects will be performed by the investigator during the screening period; during each blood pressure measurement, smoking and coffee are prohibited within 30 min before the measurement, and subjects should rest for at least 10 min. The sitting position will be taken during the measurement by placing the elbow at the same level as the heart. Each blood pressure measurement will be taken on the same side of the body;

[Pulmonary function test] Maximum vital capacity, the forced expiratory flow at 25-75% of forced vital capacity (FEF25-75), the peak expiratory flow (PEF), maximum expiratory volume per second, diffusing capacity of the lungs for carbon monoxide (DLCO) and oxygen saturation. Carried out during the screening period and then according to the judgment of the investigator in subsequent cycles;

[Imaging examination] Including CT or MRI of the chest, abdomen, and brain. The baseline tumor assessment during the screening period can be extended to up to 3 weeks before treatment. Qualified CT/MRI scan results obtained before signing the informed consent can be used for tumor assessment during the screening period. Bone scan should be performed upon clinically suspected bone metastasis. Absence of cerebral hemorrhage should be confirmed within 21 days before randomization for subjects with stable brain metastases;

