5. STATISTICAL ANALYSIS

All efficacy and safety analyses will be based on the following populations/groups:

- **Driver gene negative population:** Subjects who are negative or not tested for EGFR and also negative or not tested for ALK fusion gene are classified into negative population. Including:
 - (1) Apatinib 250 mg + SHR1210 200 mg (Stage I): subjects who are negative or not tested for EGFR and also negative or not tested for ALK fusion gene;
 - (2) Cohort 1;
 - (3) Cohort 3;

Apatinib 250 mg + SHR1210 200 mg are used in both Cohorts 1 and 3 in Stage II.

- **Driver gene positive population:** Subjects who are positive for EGFR or ALK fusion gene are classified into positive population. Including:
 - Subjects who use apatinib 250 mg + SHR1210 200 mg and are positive for EGFR or ALK fusion gene in Stage I;
 - Cohort 2: Apatinib 250 mg + SHR1210 200 mg are used in Cohort 2.
- **Cohort 4:** Apatinib 250 mg + SHR1210 200 mg are used in Cohort 4.
- **Apatinib 375 mg + SHR1210 200 mg:** Only subjects who receive apatinib 375 mg + SHR1210 200 mg in Stage I are included.

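### SAP section 5 sends every EGFR/ALK-positive subject to the driver-positive population, yet lists Cohort 3, which has no EGFR/ALK condition, whole as driver-negative

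*Protocol*

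**What the plan says.** **Cohort definitions.** Protocol section 3.1 describes "Cohort 2. Non-small cell lung cancer with EGFR mutation or ALK fusion gene rearrangement", and criterion 4 of section 5.1 admits to that cohort "Patients with confirmed presence of mutations in EGFR 18-21 exons or ALK fusion genes". Neither limits histology, whereas section 3.1 restricts Cohorts 1 and 4 to non-squamous disease. Section 5.1 defines the third cohort by histology: "Cohort 3. Imaging confirmed non-central squamous cell lung cancer or adenosquamous carcinoma primarily consisted of squamous cell carcinoma (pathologically confirmed". It sets no EGFR or ALK condition. The synopsis repeats these definitions.

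**Prior inhibitor treatment.** For Stage II the condition stands only under Cohort 2, for example "Carriers of sensitive EGFR mutations must have received at least one targeted treatment with EGFR tyrosine kinase inhibitors (EGFR-TKI) and failed the treatment", with a parallel sentence for ALK. For Stage I it covers every known positive: "The patients harboring EGFR mutations and ALK gene abnormalities must have failed the treatment with an EGFR inhibitor or ALK inhibitor".

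**Testing.** Section 7.1 says "If the subjects have not been tested previously, the study site will carry out relevant tests". Note [13] of the Schedule of Activities agrees: for subjects already tested, "retests are not required; otherwise, the study site will perform relevant tests". Neither place exempts any histology.

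**Analysis populations.** SAP section 5 bases all efficacy and safety analyses on a set of named populations. For driver-negative: "Subjects who are negative or not tested for EGFR and also negative or not tested for ALK fusion gene are classified into negative population". The list beneath names Stage I 250 mg subjects who meet that rule, then Cohort 1, then Cohort 3 without a filter. For driver-positive, the rule takes any subject positive for either gene, but its list names only Stage I 250 mg positives and Cohort 2.

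**The concern.** A patient with squamous or mainly squamous adenosquamous disease and an EGFR mutation or ALK fusion meets both cohort definitions, and nothing says which one applies. If that patient is enrolled in Cohort 3, the SAP's rule and its list give different answers about the analysis population. Two programmers could build different driver-negative sets from the same text. The study is open-label, so an unsettled rule could be settled after responses are known.

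Separately, Cohort 1 requires a confirmed absence of both alterations, but the SAP pools those confirmed negatives with subjects of unknown status and plans no separate row or sensitivity analysis.

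At stake is what the driver-negative and driver-positive labels mean. They carry the tabulated ORR, PFS, OS and safety results, and they recur in the exploratory and subgroup analyses (SAP 5.3.10 and 5.3.11).

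**Working it through.** **Step 1. Compare the two cohorts (protocol 3.1 and 5.1).**

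| | Histology condition | EGFR/ALK condition | Stage II inhibitor-failure condition |
|---|---|---|---|
| Cohort 2 | none beyond NSCLC | positive | sensitive EGFR mutations; ALK fusions |
| Cohort 3 | squamous or mainly squamous adenosquamous | none | none |

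The definitions overlap for positive squamous and adenosquamous patients, and none of the exclusion criteria in 5.2 removes the overlap.

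**Step 2. Apply the SAP's rule and its list to each type of subject.**

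| Subject | By the rule | By the list |
|---|---|---|
| Cohort 1 | negative | negative |
| Cohort 2 | positive | positive |
| Stage I 250 mg, positive | positive | positive |
| Stage I 250 mg, untested | negative | negative |
| Cohort 3, documented negative | negative | negative |
| Cohort 3, untested | negative | negative |
| **Cohort 3, positive** | **positive** | **negative** |

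Only the last row conflicts.

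**Step 3. Find who can be untested.** Cohorts 1, 2 and 4 each need a known status to qualify. Among subjects in the driver-gene populations, that leaves the Stage I 250 mg group and Cohort 3. Testing is required there too, so an untested subject means that a required step was missed. The one permitted omission, ALK testing after a positive EGFR result, concerns subjects who are positive anyway.

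**Step 4. Reproduce the plan's figures (protocol 13.1).** At ORR 30%, the smallest n with an exact (Clopper-Pearson) 90% interval no wider than 0.30 is 30 (width 0.2987). Allowing for 20% dropout, 30/0.8 = 37.5, so 38 per cohort, as stated. The total is 78 + 38 + 38 + 20 = 174, as stated. This point disputes none of these figures.

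**Step 5. Illustrate the size.** The documents give no EGFR/ALK prevalence for Cohort 3 and no ORR for such patients. Assume k positives among the 38, with ORR p in place of 30%. The fall in expected ORR in a group of N subjects is k × (0.30 − p)/N.

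| Assumption | Cohort 3 (N = 38) | Cohorts 1 + 3 (N = 78 + 38 = 116) |
|---|---|---|
| k = 1, p = 15% | 0.15/38 = 0.4 points | 0.15/116 = 0.1 points |
| k = 4, p = 5% | 1.00/38 = 2.6 points | 1.00/116 = 0.9 points |

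If p were 30%, which is the plan's own assumption for Cohort 2 as well as Cohort 3, the fall would be zero. Stage I subjects are left out of the 116 because their number by genotype is not given. Adding them would enlarge the denominator and shrink the shift.

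**Step 6. Move one subject.** With 35 responders in 116 (30.2%), taking out one positive responder gives 34/115 = 29.6%, down 0.6 points. Taking out one positive non-responder gives 35/115 = 30.4%, up 0.3 points.

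**The case against.** The best defence is that SAP section 5 states its rule by test result before it gives any list. Read that way, a known-positive Cohort 3 subject is already driver-positive and the list is loosely worded. This stands in part. A reader might infer that the SAP directs positives into the negative population; it does not. It says two incompatible things, and nothing says that the rule overrides the list.

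Other stronger readings also fail:

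- **That the Cohort 3 ORR no longer describes its population.** Cohort 3 is defined by histology and is not labelled driver-negative. A positive squamous patient still belongs to the cohort as written.
- **That inhibitor-naive positives can enter throughout the study.** The gap is confined to Stage II Cohort 3; Stage I has its own condition for known positives. Nor did the design clearly mean to exclude all such patients. For EGFR, Cohort 2 demands inhibitor failure only of carriers of sensitive mutations, while any exon 18-21 mutation qualifies for entry.
- **That untested subjects are a large group.** Required testing makes them a fallback category. Cohort 1, the only cohort sized against an ORR benchmark, is untouched.
- **That a formal driver-gene comparison is compromised.** SAP section 3 disclaims hypotheses and inference, and the paired survival curves it plans compare the 250 mg and 375 mg doses.

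The SAP also has a driver-negative non-squamous group that leaves out Cohort 3. It avoids the overlap, though it still takes untested Stage I 250 mg subjects and applies no histology filter to the Stage I part.

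**Conclusion.** The point holds as an internal contradiction in SAP section 5, made possible by overlapping Stage II cohort definitions in the protocol. A positive Cohort 3 subject is driver-positive by the rule and driver-negative by the list. Pooling untested subjects with negatives is a lesser fault that should touch few subjects, in the Stage I 250 mg group and Cohort 3.

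The true size cannot be derived from the documents and is probably small. The illustrated falls, 0.4 to 2.6 points in Cohort 3 and 0.1 to 0.9 points in Cohorts 1 and 3 together, rest on assumed values: 1 to 4 positives with an ORR of 5-15%. The planned 90% interval for Cohort 3 is 30 points wide. The correction is justified because population membership should be fixed by one rule before results are seen, and fixing it costs almost nothing.

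**What to change.** **SAP section 5.** Define the driver-gene populations by actual test result, not by cohort label. Under negative, replace the entry for Cohort 3 with Cohort 3 subjects not positive for EGFR or ALK. Under positive, add Cohort 3 subjects who are positive. Show untested subjects as a separate row, and repeat driver-negative ORR and PFS in subjects with documented negative results. The SAP is to be finalised before database lock, so this can still be done if enrolment is complete.

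**Protocol 3.1, 5.1 and synopsis.** The sponsor must reconcile the Cohort 2 and Cohort 3 definitions. The text should state which cohort takes precedence for a mutation-positive squamous or adenosquamous patient, and how the Stage II inhibitor-failure condition, now written only under Cohort 2, relates to Cohort 3. Which eligibility rule is right is for the sponsor to decide.

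**Cost.** The SAP change needs wording and one extra table, and no new test. A few subjects may leave the negative population. If the sponsor's decision also takes positives out of Cohort 3 without replacement, the exact 90% interval at 30% widens from 0.299 with 30 evaluable subjects to 0.304, 0.310 or 0.322 when 1, 2 or 4 are removed.
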